
Treatment fidelity. To measure treatment fidelity to ABCT, the PI and colleagues developed the 37-item Couples Treatment Integrity Rating Scale (C-TIRS (Hallgren et al., under review). Because ABCT includes interventions not relevant to B-FIT, the C-TIRS will be shortened to eliminate CBT items; other items will be reworded to assess interventions with family member rather than just an intimate partner. Sessions will be digitally recorded and rated for fidelity by graduate students trained to use the modified C-TIRS, using training and reliability procedures used previously in our lab.

Therapist selection, training, and supervision. B-FIT therapy sessions will be provided by a TLH clinician. Clinician training will include four elements: (a) didactic material on the rationale for B-FIT and each B-FIT intervention as well as a detailed description of each intervention; (b) role play rehearsal of each intervention; (c) supervised practice with the B-FIT manual with the first six patients/CFMs in which each audio-taped session will be reviewed by [name], or [name] and feedback provided to the clinician; (d) additional didactic training and role play rehearsal with the modified B-FIT protocol after the pilot testing and second round of focus groups. Treatment delivery will be monitored throughout the small clinical trial and Drs. [name], [name], and [name] will continue to listen to session tapes and give feedback to study clinicians.

Within treatment data collection. At TLH, patients and CFMs will complete measures of patient drinking since the last session, CFM level of distress, patient and CFM use of B-FIT interventions, and satisfaction with the treatment session (see Table 1). Patients and CFMs will each be compensated \$10 for completing within-treatment forms after each session.

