Follow-up. Patients and CFMs in the randomized clinical trial will be re-assessed at CASAA four months after baseline data collection (approximately 3 months after the last B-FIT session if all three sessions are completed). Persons with alcohol and other substance use disorders often have unstable lives, inconsistent living arrangements, and telephones that are turned off at times. To assist in keeping track of participants, a study locator form (Confidential Information Form) will be used. This is standard procedure in substance abuse research, and has been used in clinical trials at CASAA and elsewhere for 20 years. The form asks participants to provide personal contact information as well as contact information for relatives or friends who could assist the researchers in finding participants who cannot be located through their initial contact information. Participants give signed consent on the locator form for research staff to use the contact information (see bottom of pages 1 & 3). Specifically, on page 1, the consent reads, "I hereby grant my permission for the above information to be used to locate me if I cannot be found, for the purpose of completing a research interview. I understand that I may withdraw this permission at any time." At the bottom of page 3, participants give separate consent for the research team to contact individuals listed on the form: "I hereby grant my permission for the people I have named above to be contacted in the event that I cannot be found. I understand that the only purpose of such contact would be to locate me, and that the individuals need not be given any information about the nature of the research in which I am participating, unless I grant permission. I may at any time change these names or withdraw my permission for one or more of them to be contacted." This form is used only for participants who are continuing in the research but difficult to locate; it is not used for participants who have formally withdrawn from the study.

Patients and CFMs in the pilot study will not provide follow-up assessments. Patients and CFMs in the clinical trial each will be compensated \$40 for completion of follow-up data collection. See Table 1 for list of assessments. Some patients may still be receiving treatment services at the time of research follow-up; this information will be tracked on the Treatment Services Review (McLellan, Alterman, Cacciola, Metzger, & O'Brien, 1992).

III. Consent Procedures

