Three PES staff will be available for recruitment, data collection, and data entry. Four psychology doctoral students will be available to assist with recruitment, data collection, and data entry as needed. PES has provided participant recruitment, assessment, tracking, and follow-up services to investigators at CASAA for the past 20 years, and for approximately 75 different clinical trials. PES has collected data for studies of vulnerable populations including incarcerated juveniles and adults, opiate dependent adolescents, homeless and pregnant women, and persons receiving substance abuse treatment in residential and ambulatory treatment settings. PES has worked regularly with TLH staff for several previous studies. Thus they are knowledgeable about the data collection process and understand how to work with patients and also how to identify difficulties requiring intervention.

In addition to the availability of on-site Master's-level clinicians and medical staff at TLH, the CASAA research team includes licensed clinical psychologists who will provide backup consultation. There will be no need to utilize outside emergency resources, as our sites will fully cover these needs.

Clinicians will utilize CASAA's existing digital audio recorders to record in-session interactions. Hard copy data will transported daily from TLH to CASAA and stored in locked filing cabinets, and consent forms will be securely stored in a separate locked cabinet. All computerized data (including audio recordings) will be backed up on the CASAA server, which is firewall protected and accessible only through individual authorization and passwords. Data will be analyzed and integrated into B-FIT materials by core research staff including the PI.

VIII. Unanticipated Problems

The ongoing interaction between TLH clinicians and medical staff, patients and their families, and CASAA research staff will help to ensure that if there are any adverse clinical events they will be identified and dealt with swiftly. It will be made clear during training that any adverse events need to be dealt with locally and quickly and that the PI (a licensed clinical psychologist) should be notified during the event if need be, or the same day if it is not an emergency. Any unanticipated adverse events will be recorded, and an adverse event form will be completed and submitted to the UNM IRB within seven days.

EXPECTED RISKS/BENEFITS

I. Risks

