We believe the risks in this research are minimal. We foresee no physical risks as a result of participating in the research project. Similarly we foresee no direct financial or legal risks as a result of participating in the research study. Clients may be involved with the criminal justice system, but that involvement is overseen by other entities and is not a part of the research project. If we find the participant is intoxicated at baseline or follow-up assessment they will be voluntarily retained at the site until they are legally sober. There are three potential areas of risk: (1) perceived coercion to participate in the study; (2) a risk of some psychological harm in carrying out treatment studies. Participants may find answering some of the questions causes discomfort, or that participating in treatment with a family member contributes to relationship distress; (3) potential breaches of confidentiality. Methods for managing these potential risks are outlined below.

Perceived coercion: We are working with clients who may have been convicted of DWI or otherwise are involved in the criminal justice system. However, the treatment they receive as part of this research study has no bearing on the requirements they need to fulfill obligations with the court. We will make it clear both verbally and in the Informed Consent form that participation in the treatment study will neither help nor hinder their standing with the courts. Further, only clients who have voluntarily admitted themselves (i.e., are not court-mandated) to treatment at TLH will be eligible for study participation.

Although participants in this study are not prisoners, they may be involved in the criminal justice system insofar as they have been convicted for an alcohol related offense. We will make it very plain that data collected as part of the research study will not be available to the courts and will have no bearing on their status with the courts. Because they are not prisoners they will not require special protections, but we still need to be mindful that simply being involved in the criminal justice system makes them more vulnerable than a group not involved in the criminal justice system.

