More generally, it is possible that patients may believe they should participate to maintain good standing with their treatment providers. The recruitment and informed consent processes will clearly state that participation in the study intervention or subsequent withdrawal will have no impact whatsoever on their course of treatment.

Potential psychological harm: There is always a risk of some psychological harm in carrying out treatment studies. First, some of the questions in the assessment instruments may cause discomfort in some people. We have administered these measures in previous research studies and have found that they cause minimal distress to most people. If time needs to be taken so the person can compose themselves the interviewers will allow them to do so. In the unlikely case that a question causes severe discomfort, senior clinical staff from TLH will be called in and the PI will be contacted by phone. All data collection will be completed by experienced interviewers from the CASAA Program Evaluation Services (PES), who have had training in how to deal with crises, such as giving respite time, calling a clinician, and when to call a crisis center. The second potential source of psychological harm is that the provision of family-involved treatment could increase conflict in the family. Families in which there is domestic violence will be screened out of the study, so the risk of actual physical violence will be decreased substantially. One of the most consistent findings for family-involved treatment for alcohol and other substance use disorders is an increase in couples or family satisfaction and a decrease in domestic violence, and the B-FIT treatment protocol is designed to teach better communication skills,

thus mitigating the chance of increased conflict. The therapy will be given by licensed and trained counselors who have experience working with people with substance use disorders, and they will receive formal training and on-going supervision in the B-FIT protocol. If a participant (patient or CFM) finds some of the issues difficult the counselor can help them work through those issues. Furthermore, the research staff includes licensed clinical psychologists who will provide backup consultation to the therapists.

Potential breaches of confidentiality: The third risk is the possibility of a breach of confidentiality. Several steps will be taken to minimize the risk of breaches of confidentiality:

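### Only unanticipated adverse events must be recorded, so the family harms the protocol foresees have no event-level record, and passive detection gives the B-FIT arm more chances of being noticed

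*Combined protocol and SAP*

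**What the plan says.** Section VIII, Unanticipated Problems, sets two duties in consecutive sentences. Staff are to be trained that "any adverse events need to be dealt with locally and quickly", and the principal investigator is told during the event or the same day. The recording duty is narrower: "Any unanticipated adverse events will be recorded, and an adverse event form will be completed and submitted to the UNM IRB within seven days". Events are to be identified through "The ongoing interaction between TLH clinicians and medical staff, patients and their families, and CASAA research staff".

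The Risks section names harms in advance. Questions may cause discomfort, participants may find that "participating in treatment with a family member contributes to relationship distress", and "the provision of family-involved treatment could increase conflict in the family". Breach of confidentiality is listed as well.

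On contact after baseline, B-FIT adds three joint 60-minute sessions, which are recorded and reviewed. Under Within treatment data collection, "patients and CFMs will complete measures of patient drinking since the last session, CFM level of distress", along with use of B-FIT interventions and satisfaction with the session. Families in TAU usually take no part in treatment beyond weekend visits. Patients and CFMs in the RCT "will be re-assessed at CASAA four months after baseline data collection"; no other research assessment after treatment is described.

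Under Aim 2a, Family Environment Scale (FES) Conflict, reported by both patient and CFM, and the CFM's BDI and BAI totals are compared by arm at 4 months with baseline adjustment.

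**The concern.** The recording rule turns on whether an event was unanticipated, and the harms most specific to a family-involved treatment are the ones the protocol has already anticipated. Read literally, worsening conflict after a B-FIT session is handled on site and notified, but no event form is required. The protocol gives no adverse-event definition, no collection window, no event question for the 4-month visit and no table of harms by arm.

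Two consequences follow. First, the trial would not yield counts of its own named harms, although Aim 3 is to finalize all measures for a larger RCT. Second, events that do surface come from opportunistic contact. The experimental arm has more of that contact, and inpatients have little scheduled contact once they leave hospital. A raw comparison of recorded events could then make B-FIT look worse for reasons unrelated to true risk, while an absence of recorded events would say little about anticipated harms.

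**Working it through.** The plan gives no figure for harms, so there is none to reproduce. The check compares sections and adds supporting arithmetic.

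**1. Rule against foreseen harms.**
- All adverse events: managed locally and notified to the principal investigator (section VIII). No record is stated.
- Unanticipated adverse events: recorded, form sent to the IRB (section VIII).
- Relationship distress and family conflict: foreseen (Risks), hence outside the second class on a literal reading.
- Violence or severe psychopathology found after screening: leads to withdrawal (Participant Withdrawal). No event form is mentioned.
- Partner Violence Screen: described only at screening (Table 1 and the screening sections), so no later violence question is described.

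**2. Time after discharge.** Inputs: average residential stay 18-21 days (Treatment as usual); follow-up at 4 months, 4 × 30.44 = 121.8 days. If baseline falls at admission:
- 18-day stay: (121.8 − 18)/121.8 = 103.8/121.8 = 85.2%
- 21-day stay: (121.8 − 21)/121.8 = 100.8/121.8 = 82.8%

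A baseline later in the stay raises these shares. Patients from the planned intensive outpatient program may have more contact, so the figures apply to inpatients only.

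**3. Scheduled study contacts after baseline.** If the post-session forms are B-FIT only:
- B-FIT: 3 sessions + 1 follow-up = 4
- TAU: 0 + 1 = 1

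The forms follow each session and ask about B-FIT interventions, which supports that reading, but the text does not state it. The joint sessions and their recordings are B-FIT only either way.

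**4. Illustration of uneven detection.** Suppose true risk p is the same in both arms and each contact independently detects an event with probability s. Both are assumptions; the documents give no value for s. Recorded risk is p × [1 − (1 − s)^k] for k contacts, so the B-FIT to TAU ratio is [1 − (1 − s)^4]/s:
- s = 0.3: (1 − 0.7^4)/0.3 = 0.760/0.3 = 2.5
- s = 0.5: (1 − 0.5^4)/0.5 = 0.9375/0.5 = 1.9

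This ignores routine staff contact during the stay, which patients in both arms share, so it fits CFMs better than patients.

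**5. What a symmetric 4-month question could show.** Statistical power expects 34 B-FIT and 17 TAU after 15% attrition. With zero events among n, the one-sided 95% upper limit is 1 − 0.05^(1/n):
- n = 34: 8.4%
- n = 17: 16.2%

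**The case against.** The strongest reply is that the main foreseen harm is already measured evenly. FES Conflict is collected from patient and CFM in both arms and compared by two-tailed tests, which can show worsening, and CFM mood is treated likewise. This stands. A reader might infer that the anticipated harms go wholly unmeasured and that the next trial would begin with no information on them; Aim 2a does not support that. What the scores lack is event-level content. A mean difference at one time point cannot count a separation, an injury or a crisis, or tie it to a session, and scores are missing for dyads who do not return.

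A reader might also infer that detection rests on hospital staff alone. Section VIII names research staff too. Research personnel also review suicidal ideation at assessments, and possible child abuse or neglect has its own reporting route.

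It is equally tempting to state as fact that TAU has no contacts between baseline and follow-up at which harm could surface. The documents do not say so: the B-FIT-only reading of the forms is an inference, and TAU inpatients see the same hospital staff during their stay.

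Finally, section VIII is written for IRB reporting and does not forbid logging other events. A serious family rupture might be judged unanticipated and so reportable, since the protocol calls the risks minimal. The appended emergency procedures and therapy manual cannot be seen here and may require incident notes. These points soften the concern without removing it. The stated duty is restrictive, the protocol does not define where an anticipated harm ends, and nothing visible provides a uniform question or a summary by arm.

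**Conclusion.** The point holds in a limited form. The harms foreseen in the Risks section have no required event-level record and are seen only indirectly, through conflict and CFM mood scores at 4 months. Detection is passive and probably uneven between arms. For inpatients, some 83-85% or more of the four months follows the average discharge, with a single research visit at its end.

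The 2.5- and 1.9-fold ratios are illustrations under assumed detection probabilities, not estimates. The discharge share assumes baseline at admission and the average stay.

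A reader might take the 40 B-FIT dyads planned at baseline (Aim 2c) and conclude that zero events would exclude rates above 7.2%. A question asked at 4 months would be answered by about 34 and 17, so the limits are 8.4% and 16.2%. Full recording would therefore still leave any comparison of rare harms imprecise. The gain is an interpretable count with a known denominator. This is a worthwhile low-cost improvement; it does not undermine the efficacy analyses.

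**What to change.** Reword section VIII so that adverse events in patients and CFMs are recorded whether anticipated or not, from consent to the 4-month follow-up. Leave the seven-day IRB submission for unanticipated events unchanged.

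Add one short question set, identical for both dyad members in both arms, to the existing 4-month interview: for example worsened relationship, separation, injury, self-harm, and hospital or emergency visit. Tabulate that source descriptively by arm with denominators and exact limits. Report events detected in B-FIT sessions separately, so that unequal contact does not enter the comparison. State which arm completes the within-treatment forms.

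The cost is a few more minutes of interview, more event forms and one descriptive table, at a visit that is already scheduled and paid. This version is dated February 2017 and follow-up was planned for January to November 2017, so dyads seen before the change would lack the questions. Show them as not asked rather than as free of events.
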